6.1 WFHS IRB AE Reporting Requirements

Any unanticipated problems involving risks to subjects or others and adverse events shall be promptly reported to the IRB, according to institutional policy. Reporting to the IRB is required regardless of the funding source, study sponsor, or whether the event involves an investigational or marketed drug, biologic or device. Reportable events are not limited to physical injury, but include psychological, economic and social harm. Reportable events may arise as a result of drugs, biological agents, devices, procedures or other interventions, or as a result of questionnaires, surveys, observations or other interactions with research subjects.

All members of the research team are responsible for the appropriate reporting to the IRB and other applicable parties of unanticipated problems involving risk to subjects or others. The

Principal Investigator, however, is ultimately responsible for ensuring the prompt reporting of unanticipated problems involving risk to subjects or others to the IRB. The Principal Investigator is also responsible for ensuring that all reported unanticipated risks to subjects and others which they receive are reviewed to determine whether the report represents a change in the risks and/or benefits to study participants, and whether any changes in the informed consent, protocol or other study-related documents are required.

Any unanticipated problems involving risks to subjects or others occurring at a site where the study has been approved by the WFHS IRB (internal events) must be reported to the WFHS IRB within 7 calendar days of the investigator or other members of the study team becoming aware of the event.

7.0 Data Reporting

Data will be tracked and entered by study staff on a secure server. No data reporting is necessary.

8.0 Statistical Considerations

Objectives: This feasibility study, incorporating epigenetic age estimates with a nuts and EVOO intervention in individuals with MetS, is an initial step in building our understanding of the relationship between metabolic syndrome and epigenetic age and how epigenetic age estimates may be perceived by participants with MetS. This study will provide preliminary longitudinal data examining the potential to slow epigenetic age acceleration after a 4-week nuts and EVOO intervention. This longitudinal study is designed to provide pilot information that will be used to design a larger study of the effects of the nuts and EVOO on epigenetic aging. This line of work will be an important foundation towards translating epigenetic age prediction from a research concept towards a tool to meaningfully promote healthy lifestyle changes to improve cardiometabolic health among individuals at high risk for cardiovascular disease.

8.1 Prevalence of epigenetic age acceleration

Primary Outcome 1: proportion of participants with MetS with advanced epigenetic aging

To characterize the relationship between MetS and epigenetic aging, we will examine epigenetic age acceleration prevalence among the 50 participants with metabolic syndrome. Epigenetic age acceleration will be calculated as described in 5.2. Advanced epigenetic age acceleration will be defined as a positive epigenetic age acceleration (higher than expected based on chronological age).

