DNA methylation patterns change with age, and can be used to estimate chronological age [9-12]. A greater DNA methylation-based predicted age relative to chronological age, often referred to as "**epigenetic age acceleration**", has been associated with many lifestyle factors, including physical activity and diet, as well as components of MetS, including obesity, blood pressure, HDL cholesterol and blood glucose levels [13]. A higher number of MetS components are cross-sectionally associated with epigenetic age acceleration [14]. Epigenetic age acceleration is more strongly predictive for the risk of morbidity and mortality than chronological age [9, 11]. We **hypothesize** that the majority of people with MetS have advanced epigenetic aging, and among those that have advanced epigenetic age, learning about epigenetic age and its relationship to morbidity and mortality at the onset of a dietary intervention will improve participant adherence to the dietary intervention. Further, we hypothesize that daily consumption of EVOO and tree nuts in participants with MetS and advanced epigenetic age could help reverse MetS and potentially slow epigenetic aging. Therefore, we plan to conduct this feasibility pilot study to:

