2.1 Inclusion Criteria

- 2.1.1 Men and Women \geq 35 years of age
- 2.1.2 Metabolic syndrome, defined as \geq 3 of the following:

- 2.1.2.1 Waist circumference >102 cm in men and >88cm in women
- 2.1.2.2 Triglycerides >150 mg/dL AND/OR drug treatment for elevated triglycerides
- 2.1.2.3 HDL cholesterol <40 mg/dL in men and <50 mg/dL in women AND/OR drug treatment for reduced HDL cholesterol
- 2.1.2.4 Systolic blood pressure >130 mm Hg or diastolic blood pressure >85 mmHg AND/OR antihypertensive drug treatment
- 2.1.2.5 Fasting glucose >100 mg/dL or hemoglobin A1c > 5.6% AND/OR oral hypoglycemic medications
- 2.1.3 Willing to comply with study visits, as outlined in the protocol
- 2.1.4 Able to read and speak English
- 2.1.5 No allergies or hypersensitivities to olive oil or nuts
- 2.1.6 Ability to understand and the willingness to sign a written informed consent document.
- 2.1.7 Completion of a validated 14-item Mediterranean Diet Assessment Screener to assess baseline dietary consumption of nuts and olive oil

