5.2 Blood-based Biomarkers

HDL cholesterol, triglycerides, HbA1c, and fasting glucose levels will be analyzed using serum samples at a local LabCorp facility.

Epigenetic age acceleration: DNA methylation will be measured from blood samples frozen/ stored at -80 C within 2 hours of collection. After recruitment of 50 participants meeting the criteria for MetS is completed, blood samples will be sent for DNA methylation analysis in the lab of [name] at WFBMC. DNA will be extracted from whole blood samples, and will be bisulfite-converted using the EZ DNA Methylation Gold kit (Zymo, Irvine, CA). Illumina Infinium MethylationEPIC BeadChip, which targets over 850,000 CpG sites, and the Illumina iScan Reader will be used to determine the proportion of DNA methylation at each site. The ratio of the fluorescence intensity of the methylated versus the combined methylated and unmethylated probes will be determined with Illumina GenomeStudio. As a quality control measure, the cumulative fluorescent signal must be significantly greater than the negative controls included for each sample. We will use a threshold of this "detection p-value" of ≤ 0.05 in at least 90% of the samples as criteria for adequate assays. Finally, adjustments will be made to normalize the fluorescent signals from the Infinium I and Infinium II fluorescent assays used prior to analysis (in Bioconductor).

DNA methylation profiles (beta-value, after adjustment chip and position effects) at 1,030 unique DNA methylation profiles will be used for epigenetic age acceleration predictions, using the DNA GrimAge predictor [11]. We will calculate predicted lifespan and regress predicted lifespan on chronological age to produce estimates of epigenetic age acceleration.

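### Section 8.1 sets out to characterise how MetS relates to epigenetic aging, but a proportion among 50 people who all have MetS, with no named reference for expected age, cannot do that

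*Combined protocol and SAP*

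**What the plan says.** Section 8.1 gives an aim and one analysis for Primary Outcome 1: "To characterize the relationship between MetS and epigenetic aging, we will examine epigenetic age acceleration prevalence among the 50 participants with metabolic syndrome". The outcome is binary: "Advanced epigenetic age acceleration will be defined as a positive epigenetic age acceleration (higher than expected based on chronological age".

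Section 5.2 describes the calculation. The analyst will "regress predicted lifespan on chronological age to produce estimates of epigenetic age acceleration". It does not say whether that line is fitted to the 50 participants or taken from another population.

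MetS, meaning at least three of five components, is an entry requirement (section 2.1.2). Section 5.2 adds: "After recruitment of 50 participants meeting the criteria for MetS is completed, blood samples will be sent for DNA methylation analysis". No analysis of people without MetS is planned.

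Two other places bear on the aim. Section 8.0 says more cautiously that the study "is an initial step in building our understanding of the relationship between metabolic syndrome and epigenetic age". Section 1.0 gives as background: "A higher number of MetS components are cross-sectionally associated with epigenetic age acceleration". Section 8 does not use the component count. Objective 1.1 asks only for the proportion.

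**The concern.** A relationship with MetS needs some contrast in MetS: people with and without it, people with more or less of it, or an outside benchmark. Section 8.1 has none of these. One percentage from an all-MetS sample could be 40% or 70% for reasons unrelated to MetS, and nothing in the plan would tell these apart.

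At stake is the reading of a primary outcome. As worded, a bare percentage could be reported as evidence that MetS and epigenetic aging are linked. If the age line is internal, even the percentage carries almost no information. Cutting acceleration at zero also discards its size, although the continuous value is available for every participant.

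**Working it through.** **The plan's own power figure.** Section 8.6 gives 0.80 power with 50 people, alpha 0.05 and a difference of 0.4 SD. For a two-sided one-sample or paired test, power = Φ(0.4 × √50 − 1.96) = Φ(0.868) = 0.807; the exact t calculation gives 0.792. The figure reproduces. It concerns a mean difference and says nothing about an association with MetS.

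**Can a MetS effect be estimated?** With all 50 participants MetS-positive, the MetS indicator equals 1 for everyone and duplicates the intercept. The design matrix has rank 1, so no MetS coefficient exists.

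**What if the age line is fitted within the sample?** Least-squares residuals sum to zero. Adding a constant shift to every predicted age moves the fitted intercept by that constant and leaves each residual unchanged, so the share of positive residuals cannot respond to the shift. In a simulation of 50 people (assumed: ages uniform from 35 to 75, slope 0.9, normal residuals with SD 4), the share averaged 50% with a 95% range of 42-58%. The result was the same for true shifts of 0, 0.5, 1 and 2 residual SD.

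**What if the age line is external?** No shift then gives about 50% positive. Assuming normality, a shift of 0.5 SD gives Φ(0.5) = 69%. An exact two-sided binomial test against 50% with n = 50 rejects at 33 or more, or 17 or fewer, and has about 74% power. Exact 95% intervals for the proportion would be:

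| Positive | 95% CI |
|---|---|
| 25/50 | 35.5-64.5% |
| 30/50 | 45.2-73.6% |
| 35/50 | 55.4-82.1% |

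**What can the collected data support?** Waist, blood pressure, medication names and fasting blood are taken at baseline (section 4.3.1), and HDL, triglycerides, HbA1c and glucose are assayed (section 5.2). The count of components met is therefore available and takes the values 3, 4 or 5.

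Suppose acceleration is A = Y − (c + d × age) for some reference line. Regressing A on count, age and sex changes the intercept by c and the age coefficient by d, and leaves the count slope unchanged. With age in the model, the slope is the same for any reference that is linear in age.

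**How precise is that slope?** By Fisher's z, the correlation detectable with 80% power at two-sided 0.05 is tanh((1.96 + 0.842)/√47) = 0.387. Power at r is Φ(atanh(r) × √47 − 1.96), which gives 0.28 at r = 0.20 and 0.56 at r = 0.30.

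The mix of 3, 4 and 5 components is not in the documents, so a range is assumed. With residual SD set to 1, the detectable slope comes from the noncentral t distribution on 48 df with noncentrality b × SD × √50. The CI half-width is 2.011/(SD × √50). Both are before adjustment for age and sex.

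| Assumed 3/4/5 mix | SD of count | Slope at 80% power | 95% CI half-width |
|---|---|---|---|
| one third each | 0.82 | 0.50 | 0.35 |
| 50/30/20% | 0.78 | 0.52 | 0.36 |
| 60/30/10% | 0.67 | 0.60 | 0.42 |
| 70/25/5% | 0.57 | 0.71 | 0.50 |

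**The case against.** The best defence is that the plan delivers its objective. Objective 1.1 asks for a proportion and Primary Outcome 1 is that proportion. Section 8.0 claims only a first step, and section 8.6 concedes limited power. No objective asks for an association with component count. This stands: the fault lies in the opening clause of section 8.1 and in the undefined reference, not in a missed objective.

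A reader might infer that the proportion can never say anything about MetS, whatever reference is used. That goes too far. Against an external age line, the proportion becomes a one-sample comparison with that population. This is indirect and depends on the populations and assays being comparable, but it is a contrast, and it fits the section 1.0 hypothesis that most people with MetS are epigenetically older than their years. The difficulty is that no such reference is named.

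A reader might also infer that regression on component count recovers the relationship named in section 8.1. It does not. Entry at three or more components cuts off the lower range, so MetS versus no MetS remains unidentified.

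Nor is the regression without drawbacks. It is weakly powered at plausible correlations, and section 1.0 gives no effect size to suggest a value near 0.39.

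Finally, section 3.1 has blood drawn from everyone who consents, which might include people who prove not to have MetS. The documents do not plan to assay or analyse them as a comparison group.

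**Conclusion.** The point holds. Section 8.1 claims more than its single analysis can support, because there is neither a group without MetS nor a named external reference. Under an internal age fit the proportion is fixed near 50% (42-58%); the residual share's insensitivity to a constant shift is algebraic, while the range rests on the simulation's assumptions. Under an external reference the proportion would be informative but indirect.

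The component-count slope can be estimated from data already collected, and with age in the model it is unaffected by the choice among age-linear references. It describes severity within MetS and is imprecise: about 0.50-0.60 residual SD per component is detectable for mixes from one third each to 60/30/10%, and 0.71 for 70/25/5%. Those mixes are assumptions. The analysis belongs among the exploratory ones, as an estimate with its interval and not as a test expected to succeed.

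**What to change.** In section 8.1:

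1. Restate the aim as estimating the proportion of participants with MetS who have positive acceleration, reported with a 95% CI. Delete the claim that this characterises the relationship with MetS.
2. State, here and in section 5.2, that expected age comes from a named external reference and not from a line fitted to the 50 participants.
3. Add, labelled exploratory, a linear regression of continuous baseline acceleration on the number of components met under section 2.1.2, adjusted for age and sex. Report the slope with a 95% CI, and say that it is a gradient across 3 to 5 components within MetS, not a comparison of MetS with no MetS.

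The cost is a few sentences, the choice of a reference, and one extra model. No new measurement is needed. The regression does not remove the need for the reference, because the proportion still depends on it.

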3.1 Epigenetic Age Acceleration

For all participants providing informed consent, blood samples will be collected at each in-person visit to calculate epigenetic age acceleration.

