4.3.2 Intervention visit

Eligible participants (those that provided informed consent, were fasting at the in-person visit and met the criteria for MetS, and provided blood samples for epigenetic age acceleration

measurements) will be contacted to schedule the intervention visit. The study is set to end on March 21, 2022, which means the study intervention visits need to be completed by March 3, 2022. Participants that have not attended their intervention visit by March 3, 2022 will be discontinued from the study.

At the intervention visit, participants will have a fasting blood collection. Participants will receive counseling and recipes to help them incorporate the nuts and EVOO into daily meals. Dietary adherence diaries will be given to participants to measure incorporation of the study foods and participants will be instructed to complete the adherence diaries on a daily basis. Participants will be given a 4-week supply of EVOO, tree nuts, and a tablespoon for measuring the EVOO.

Participants will be randomized to learn about epigenetic age acceleration (arm 1) or to not learn about epigenetic age acceleration (arm 2) in a 1:1 allocation at the baseline visit. Those in arm 1 will receive some educational materials and a brief explanation of epigenetic age acceleration. At the end of this visit, all participants will be scheduled for the remainder of their telephone and in person study visits.

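### Primary Outcome 1 names no reference for expected epigenetic age; if the 5.2 regression is fitted to the study's own participants, the proportion positive cannot register a MetS-wide shift that is constant or linear in age

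*Combined protocol and SAP*

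**What the plan says.** Section 8.1 makes the proportion of MetS participants with advanced epigenetic ageing the first primary outcome. The cut-off reads: "Advanced epigenetic age acceleration will be defined as a positive epigenetic age acceleration (higher than expected based on chronological age". The method is given by reference: "Epigenetic age acceleration will be calculated as described in 5.2". Section 5.2 then says: "We will calculate predicted lifespan and regress predicted lifespan on chronological age to produce estimates of epigenetic age acceleration". No fitting sample, reference cohort or set of coefficients is given in either section or elsewhere.

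On the data available for a fit, 5.2 says: "After recruitment of 50 participants meeting the criteria for MetS is completed, blood samples will be sent for DNA methylation analysis". Section 3.1 adds: "For all participants providing informed consent, blood samples will be collected at each in-person visit to calculate epigenetic age acceleration". Section 4.3.2 invites back those who, among other conditions, "met the criteria for MetS, and provided blood samples for epigenetic age acceleration" measurements. Blood is therefore drawn before MetS is confirmed, and a few samples from people without MetS may exist. No section makes them a comparison group.

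Other sections use a different scale. Section 1.0 describes acceleration as "A greater DNA methylation-based predicted age relative to chronological age". Section 8.6 states its power for the gap between epigenetic and chronological age, and Appendix D explains the concept to participants in the same way. The hypothesis in 1.0 is that "the majority of people with MetS have advanced epigenetic aging". Section 8.6 says the pilot will supply prevalence estimates for planning a larger trial.

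**The concern.** A residual is positive only relative to the line it is measured from. If that line comes from an outside population, a positive value means older than that population at the same age, and a high proportion says something about MetS. If the line is fitted to the MetS participants themselves, a positive value means older than the average study participant of that age. The MetS effect then sits in the fitted line and not in the residuals.

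The plan does not say which applies, and the only samples it describes for assay point to the second. In that case the first primary outcome would return a figure that looks like a prevalence but reflects only the shape of the residual distribution. A value near 50% could be read as evidence against the majority hypothesis, or carried into the design of the next trial, although it would have been much the same under any common shift.

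**Working it through.** **Inputs from the documents.** n = 50 with MetS (8.1); cut-off above zero (8.1); clock output regressed on chronological age (5.2); lower age limit 35 (2.1); power 0.80 for 0.4 SD at α = 0.05 (8.6).

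**Assumptions, not in the documents.** Ages uniform from 35 to 75; clock = age + shift + error; normal errors with SD 5 years (3 and 7 also tried); 10,000 simulated samples per case.

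**1. The plan's own figure.** For a two-sided one-sample or paired test of a mean, power = Φ(0.4 × √50 − 1.960) = Φ(2.828 − 1.960) = Φ(0.868) = 0.807; the noncentral t gives 0.792. The stated 0.80 is reproduced. It concerns a mean gap between epigenetic and chronological age, not the proportion in 8.1.

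**2. Algebra of an in-sample fit.** Let y = a + b·age + (δ + γ·age) + e, where δ + γ·age is the shift shared by all participants. Least squares with an intercept puts δ into the intercept and γ into the slope. The residuals are those from regressing e on age alone, so they sum to zero and contain neither δ nor γ. The result is exact for shifts constant or linear in age. For any other shared shift, only the constant and linear part is absorbed.

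**3. Check on one simulated data set** (n = 50, ages 35 to 80, SD 4.5, slope 0.8). Adding 0, 2, 5 or 10 years to everyone left 26 of 50 in-sample residuals positive each time. Against a fixed line the counts were 25, 34, 43 and 50. A shift of 0.1 year per year of age also left the in-sample count at 26.

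**4. Expected proportion positive, n = 50, SD 5.** For a fixed, correctly calibrated line it is Φ(shift/5).

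| True shift (years) | Fitted in-sample | Fixed line |
|---|---|---|
| 0 | 50% | Φ(0) = 50% |
| 2 | 50% | Φ(0.4) = 66% |
| 5 | 50% | Φ(1) = 84% |
| 10 | 50% | Φ(2) = 98% |

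The in-sample 95% range is 42–58% (21 to 29 of 50) at every shift, and the same with SD 3 or 7; at n = 40 it is 40–60%. More than half positive occurs in 40–42% of in-sample data sets at every shift.

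**5. Residual shape.** With gamma errors (shape 2, scaled to SD 5), the in-sample proportion is 41% for right skew and 59% for left skew, the same to within 0.001 at shifts of 0, 5 and 10 years. The skew is illustrative; the documents say nothing about it.

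**6. What a fixed yardstick leaves open.** If the reference is wrong by c years, the proportion is Φ((shift − c)/5).
- Shift 0: c = ±1 gives Φ(∓0.2), or 42–58%; c = ±2 gives Φ(∓0.4), or 34–66%.
- Shift 5: c = ±1 gives Φ(0.8) to Φ(1.2), or 79–88%; c = ±2 gives Φ(0.6) to Φ(1.4), or 73–92%.
- Predicted minus chronological age with no MetS effect and a clock offset of −5 to +5 years: Φ(−1) to Φ(1), or 16–84%.

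**The case against.** The strongest reply is that the harm depends on a fit the plan does not state. Section 5.2 names a published clock, and its source may supply a reference; that cannot be seen from the documents. The cut-off wording in 8.1 would also suit a direct comparison with chronological age, and 1.0, 8.6 and Appendix D all use that comparison, on which a shared shift would register. A reader might infer that the plan commits to an in-sample regression and so contains a proven error. The text does not go that far. What stands is that 8.1 hands the calculation to a regression, no reference for it is named, and the only samples described for assay are those of the MetS participants.

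A reader might also infer from the lifespan wording in 5.2 that the sign of the outcome is reversed. Sections 1.0 and 8.1 already give the direction (older than expected is positive), so this is loose wording to correct.

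Nor do the documents show the 8.6 power to be wrong: it is in SD units and reproduces. Only its label needs to match the chosen definition.

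This is a feasibility pilot that admits limited power. Section 8.1 sets no test or threshold, so the share of samples above one half illustrates the hypothesis in 1.0 and is not a rule of the plan. Eligibility and randomisation do not use the acceleration value. These points limit the consequences. They do not rescue the outcome, because small numbers excuse imprecision but not a measure that cannot respond to the effect of interest, and prevalence is a stated primary objective.

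Finally, the raw difference is confounded with clock offset. That is correct: it responds to a shift, but cannot by itself attribute the shift to MetS.

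**Conclusion.** The concern holds as a conditional one. Two things are established: no reference for expected epigenetic age is named, and 5.2 and 8.1 define acceleration on a different scale from 1.0, 8.6 and Appendix D. The in-sample fit is inferred. If it is used, the loss of any shift constant or linear in age is exact and needs no distributional assumption. The size, about 50% positive with a 95% range of 42–58% at n = 50 for true shifts of 0 to 10 years, assumes symmetric (here normal) residuals; skew moves the level but does not restore a response to the shift. A correctly calibrated fixed line would give 50%, 66%, 84% and 98% at shifts of 0, 2, 5 and 10 years if the SD is 5.

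On that reading Primary Outcome 1 can neither inform the majority hypothesis nor supply the promised prevalence. The definition of a primary outcome should not be left in this state. The adherence and perception outcomes are not affected.

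**What to change.** In 5.2 and 8.1, define Primary Outcome 1 against a yardstick not fitted to these participants:

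- a named, fixed external reference equation, if a suitable one exists (the documents give none); or
- otherwise, clock-predicted age minus chronological age, the quantity 8.6 already names.

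Under either option:

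- Report mean acceleration with its 95% CI beside the proportion. At n = 50 and SD 5 the half-width is about 2.01 × 5/√50 = 1.4 years.
- Add a sensitivity analysis for a reference wrong by 1 to 2 years.
- State that the proportion bears on the majority hypothesis only under a calibration assumption. With the raw difference, clock offset cannot be separated from a MetS effect.

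Editorial changes: in 5.2, replace the reference to lifespan with the clock's predicted age, matching the direction in 8.1, and align the label in 8.6 with the definition chosen.

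The cost is protocol wording and a few lines of analysis code. The raw difference needs no new samples or assays. The external equation is equally cheap only if a suitable one exists. The downside is that the proportion then depends on clock calibration, which neither option removes.
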